9.8.2 Secondary Efficacy Endpoints

Descriptive statistics will be presented for each time point at which the variable is measured (see [Table 1](#)) for the secondary efficacy endpoints. Binary secondary efficacy endpoints will be analyzed with the same method (stratified Cochran-Mantel-Haenzel test) as the primary efficacy endpoint. Continuous secondary efficacy endpoints will be analyzed with an ANCOVA model with change from baseline as the outcome variable; treatment group, presence or absence of T2DM at baseline, and baseline NAS separated into 2 groups (NAS={4,5} or NAS={6,7,8}) as factors and baseline values as a covariate. Endpoints include:

- Change from baseline to Week 48 on liver histology as measured by the individual NAS components (ballooning, inflammation, steatosis).
- Change from baseline to Week 48 on hepatic steatosis as measured by MRI-HFF.
- Change from baseline to Week 48 on liver histology as measured by fibrosis stage. (NASH CRN)
- Resolution of NASH (defined as an overall histologic interpretation of no fatty liver disease or simple steatosis without steatohepatitis or isolated steatosis without steatohepatitis) without worsening of fibrosis as assessed by liver histology at Week 48.
- Change from baseline to Week 48 on serum liver-related biochemistry as measured by:
 - alanine aminotransferase (ALT)
 - aspartate aminotransferase (AST)
 - alkaline phosphatase (ALP)
 - gamma glutamyl transferase (GGT)
 - total bilirubin (TB)
- Change from baseline to Week 48 on metabolic indicators as measured by:
 - fasting serum glucose levels
 - insulin levels
 - HbA1c
- Change from baseline to Week 48 on serum lipids measured by:
 - fasting total cholesterol

- HDL-C
- LDL-C
- triglycerides

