7.1.3 Treatment and Assessment Period (Visits 3 through 9/EOS)

During the 48 weeks of double-blind treatment, 7 clinic visits are scheduled to occur as follows:

- Visit 3 - Week 2, Day 14 (+/- 3 days)
- Visit 4 - Week 4, Day 28 (+/- 3 days)
- Visit 5 - Week 8, Day 56 (+/- 5 days)
- Visit 6 - Week 12, Day 84 (+/- 5 days)
- Visit 7 - Week 24, Day 168 (+/- 7 days) – Interim Analysis
- Visit 8 - Week 36, Day 252 (+/- 7 days)
- Visit 9 - Week 48, Day 336 (+/- 7 days) – End of Study

Subjects are reminded not to eat and not to take their study drug on the day of scheduled study visits prior to completion of assessments. They should bring their study drug with them to the visit. All assessments should be completed at least 30 minutes prior to administration of the IP. IP should be taken 30 minutes prior to the first meal of the day containing approximately 10-20 grams of fat.

The Schedule of Assessments provided in [Table 1](#) details the procedures to be completed at each visit. All Treatment visits (3 through 9) will include weight and waist/hip measurements, assessment of vital signs, and blood sampling for completion of biochemistry, hematology, serum glucose, lipid panel, HbA1c, and serum liver-related blood tests. At all visits, adverse events, and concomitant medications will be collected for all subjects, and female subjects of childbearing potential will have a urine pregnancy test. Subjects will return containers of unused study drug for assessment of accountability and compliance which will be documented in the IRT. New supplies of study drug will be dispensed at Visits 3 through 8.

Additional assessments will also occur less frequently during the Treatment Period for vitamin A, vitamin D, vitamin E, vitamin K via PT/INR, insulin, thyroid testing, urinalysis, ECG, physical examinations, stool assessment, and completion of the EQ-5D-5L.

An MRI will be repeated at Visit 7 for the 24-week IA and at Visit 9 (Week 48) for all subjects. A final liver biopsy will be performed at Visit 9 (Week 48) for all subjects unless a subject discontinues prior to Week 44, in which case the EOS liver biopsy is not required.

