7.2.3.6 Additional Laboratory Assessments

Laboratory samples will be collected and assessed for:

- HIV testing and assessment of Hepatitis B/C including HBcAb, HBsAg, HBVDNA, and HCVA_b, and HCVRNA will occur at the screening visit only
- Lipid panel including fasting total cholesterol, HDL-C, LDL-C, and triglycerides at each scheduled study visit (Visits 1 through 10)
- HbA1c will be tested at every scheduled visit (Visits 1 through 10)
- Full coagulation panel will be done at screening and baseline, but only PT/INR is required at remaining time points at Visits 4, 7, and 9
- Insulin will be tested at screening, baseline, at Visit 4 and Visits 6 through 10
- HOMA-IR and HOMA-%B: will be calculated programmatically from serum glucose tested at screening, baseline, Visits 7, 9, and 10

- Vitamin A, Vitamin D, Vitamin E, and Vitamin K (via PT/INR) will be tested at screening, baseline, and Visits 4, 7, and 9
- Thyroid testing including TSH and T3 will be tested at screening, baseline, and Visits 4, 6, 7, 9, and 10
- C4 samples will be collected at baseline and Visits 6, 7, 9, and 10

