9.7 Study Population

The Screened Set will consist of all subjects who have signed an informed consent.

The Safety Analysis Set will consist of all subjects who take at least 1 dose of randomized IP, and have at least 1 post-baseline safety assessment (eg, coming back for any visit, reporting of an AE or reporting the absence of AEs).

The Full Analysis Set (FAS) will consist of all subjects in the Safety Analysis Set who have at least 1 post-baseline efficacy assessment (eg, MRI, liver biopsy, serum liver-related biochemistry measurement).

The Interim Analysis Set (IAS) will consist of all subjects in the Safety Analysis Set who have at least 1 post-baseline efficacy assessment (eg, MRI, ALT biochemistry measurement) on or before the Week 24 visit at the data cut time of the IA.

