9.8.3 Exploratory Efficacy Endpoints

Descriptive statistics will be presented for each time point at which the variable is measured (see **Table 1**) for the exploratory efficacy endpoints. Binary exploratory efficacy endpoints will be analyzed with the same method (stratified Cochran-Mantel-Haenzel test) as the primary efficacy endpoint. Continuous exploratory efficacy endpoints will be analyzed with an ANCOVA model with change from baseline as the outcome variable; treatment group, presence or absence of T2DM at baseline, and baseline NAS separated into 2 groups (NAS={4,5} or NAS={6,7,8}) as factors and baseline values as a covariate. Endpoints include:

- Change from baseline to Week 48 on liver histology as measured by the SAF scoring components: Steatosis (S), Activity (A), and Fibrosis (F)
- Change from baseline to Week 48 on anthropomorphic measures:
 - body weight
 - BMI
 - waist circumference
 - waist-hip ratio
- Change from baseline to Week 48 in subjects with T2DM on homeostasis measured by:
 - Homeostasis model assessment -IR (HOMA-IR)
 - HOMA-beta cell function (HOMA-%B)

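### Laboratory and body-size endpoints measured at five to seven treatment visits are tested by a Week 48-only ANCOVA, so unless the SAP imputes, subjects without a Week 48 value do not inform the contrast

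*Protocol*

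**What the plan says.** For the secondary endpoints, Protocol Section 9.8.2 fixes the model: "Continuous secondary efficacy endpoints will be analyzed with an ANCOVA model with change from baseline as the outcome variable". The factors are treatment group, T2DM at baseline and baseline NAS group, and the baseline value is the covariate. Section 9.8.3 uses the same form for the exploratory endpoints, which include weight, BMI, waist and waist-hip ratio: "Continuous exploratory efficacy endpoints will be analyzed with an ANCOVA model with change from baseline as the outcome variable". The endpoints are defined at one time point, for example "Change from baseline to Week 48 on serum liver-related biochemistry as measured by" (ALT, AST, ALP, GGT, total bilirubin). Other time points receive descriptive statistics only.

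Section 7.1.3 sets the schedule: "During the 48 weeks of double-blind treatment, 7 clinic visits are scheduled to occur as follows" (Weeks 2, 4, 8, 12, 24, 36 and 48). It adds that "All Treatment visits (3 through 9) will include weight and waist/hip measurements, assessment of vital signs, and blood sampling for completion of biochemistry", and the same sentence goes on to glucose, lipids, HbA1c and liver tests. Insulin is taken less often. Section 7.2.3.6 says: "Insulin will be tested at screening, baseline, at Visit 4 and Visits 6 through 10".

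Section 9.8 bases all efficacy analyses on the Full Analysis Set (FAS). Section 9.7 admits to the FAS any Safety Set subject with "at least 1 post-baseline efficacy assessment (eg, MRI, liver biopsy, serum liver-related biochemistry measurement"). The missing-data text in Section 9.8.1 concerns the primary endpoint. Section 9.4 leaves the handling of missing data to the SAP, which was not available for this review.

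**The concern.** The protocol names the model itself, so this is not a detail left open. A subject with ALT at Weeks 2 to 36 but none at Week 48 belongs to the FAS. The specified ANCOVA has no term through which those earlier values can act. If the SAP adds no imputation, the analysis becomes one of subjects observed at Week 48, although it carries the FAS label. It is then unbiased only if, given baseline, T2DM and NAS group, the chance of missing Week 48 is unrelated to response or is related in a way that cancels between arms.

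The protocol gives some reason to doubt that condition:

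- Appendix 5, invoked by Section 8.1.6, stops treatment on recorded ALT or AST elevations, so a missing Week 48 ALT can follow from earlier ALT.
- Section 9.5.1 expects discontinuations for gastrointestinal events and compares them by arm.
- Section 9.8.1 allows that missingness may differ between arms, and proposes using existing HFF or ALT data for the primary endpoint. That treats interim values as informative.

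At stake are the size and precision of the Week 48 contrasts for the secondary laboratory and exploratory body-size endpoints.

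**Working it through.** **Inputs from the protocol**

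- Treatment visits after baseline: Weeks 2, 4, 8, 12, 24, 36, 48 = 7 (Section 7.1.3).
- Insulin up to Week 48: Visits 4, 6, 7, 8, 9 = 5 (Section 7.2.3.6; Visit 10 falls after treatment ends).
- Dropout 20%, with 266 randomized if three arms continue (Section 9.6).

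**Inputs assumed.** The within-subject correlation ρ and the dropout mechanism. The protocol gives neither, so a range is shown.

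**The plan's own figures.** 221 × 1.2 = 265.2, which gives the stated 266. No power is stated for the secondary or exploratory endpoints. The 67 completers per group belong to the primary endpoint: 21% against 45%, 80% power, two-sided 5% as the first Holm step and continuity correction give 68. They matter here only for arm size: 67 / 0.80 = 83.75, so 84 per arm.

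**Subjects concerned.** 0.20 × 266 = 53.2, about 53 subjects. Reading the plan's 221 as completers gives 266 − 221 = 45.

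**Precision when dropout is completely random (MCAR).** Variance of the Week 48 contrast relative to complete data, with dropout d:

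- Observed-case ANCOVA: 1/(1 − d) = 1/0.8 = 1.25.
- Repeated-measures likelihood: 1 + [d/(1 − d)](1 − ρ²) = 1 + 0.25(1 − ρ²).

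| ρ | Repeated-measures variance | SE ratio to ANCOVA |
|---|---|---|
| 0.3 | 1.228 | 0.991 |
| 0.5 | 1.188 | 0.975 |
| 0.7 | 1.127 | 0.950 |
| 0.8 | 1.090 | 0.934 |

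For ρ = 0.5: √(1.188/1.25) = 0.975. The standard error falls by about 1-7%.

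**Bias, by simulation.** The set-up was 84 per arm, changes at Weeks 12, 24, 36 and 48 with residual SD 1 and common correlation ρ, a true difference of 0, and 3,000 trials per row. Dropouts leave after Week 12, at about 20% in each arm. In the MAR and MNAR rows active subjects leave at random. Placebo subjects leave more often when their Week 12 value is poor (MAR: dropout depends on recorded data) or when their Week 48 value is poor (MNAR: dropout depends on unseen data). The repeated-measures estimate is the likelihood estimate for this missing pattern: regress Week 48 on arm, baseline and Week 12 among those observed, then predict for everyone. Positive values count against the active arm. The simulation error of each mean is about 0.18/√3000 = 0.003.

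| Mechanism | ρ | Observed-case ANCOVA | Repeated measures |
|---|---|---|---|
| MCAR | 0.4 / 0.6 / 0.8 | 0.000 / 0.001 / −0.001 | 0.000 / 0.001 / −0.001 |
| MAR | 0.4 / 0.6 / 0.8 | 0.081 / 0.118 / 0.162 | 0.003 / −0.002 / 0.003 |
| MNAR | 0.4 / 0.6 / 0.8 | 0.202 / 0.199 / 0.201 | 0.171 / 0.130 / 0.075 |

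**The case against.** A reader might infer that the protocol discards dropouts' data. It does not say so. It fixes a model, not a missing-data rule. Multiple imputation from earlier visits followed by this same ANCOVA would comply with Sections 9.8.2 and 9.8.3, and Section 9.4 leaves missing data to the SAP. Section 7.2 also asks for reasonable effort to obtain end-of-study assessments at early termination. This stands, and makes the concern conditional on the SAP. It does not dispose of it: an early-termination value is not a Week 48 value, and entering it as one would amount to carrying the last observation forward.

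A reader might also infer that a repeated-measures model removes the bias. That holds only under MAR. Under MNAR the bias is reduced, and under MCAR there is none to remove.

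A third tempting reading is that about a third of the effect is lost. A scenario can be built that shows this: 81 per arm, 16-19% dropout, placebo dropout driven by a poor last value, and residual visit correlations of about 0.56-0.90. There the observed-case contrast averages −0.26 SD against a true −0.40 SD. It is a single assumed mechanism, and one that suits the repeated-measures model. Treatment is blinded, and nothing in the protocol shows that subjects would leave because of GGT, HDL-C or HbA1c. Gastrointestinal dropout need not track those values. The figure should not be taken as the expected size.

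Finally, Week 48 ANCOVA is a standard method. The primary endpoint is histologic, and the interim decision uses Week 24 data under its own criteria. This stands and limits the weight of the point.

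**Conclusion.** The point holds as a modest, nearly free improvement to secondary and exploratory analyses. The protocol fixes a model that uses no intermediate visits for endpoints measured at seven treatment visits (insulin at five). Unless the SAP imputes, about 53 of 266 subjects would not inform the Week 48 contrast.

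The size depends on assumptions that the protocol cannot settle. For ρ of 0.4-0.8 and about 20% dropout, the bias of observed-case ANCOVA is about 0.08-0.16 SD under arm-dependent MAR dropout, against about 0 for repeated measures. Under MNAR it is 0.20 SD, against 0.08-0.17 SD. Under MCAR there is no bias, and for ρ of 0.3-0.8 the standard error falls by about 1-7%. The direction shown follows from letting poor placebo responders leave; another mechanism could reverse it. Repeated measures was no worse than observed-case ANCOVA in any scenario tried.

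**What to change.** In Sections 9.8.2 and 9.8.3, for the laboratory and anthropometric endpoints scheduled at several post-baseline treatment visits, replace the ANCOVA with an MMRM on change from baseline. It should include treatment by visit, baseline by visit, T2DM and NAS-group factors, and an unstructured covariance with a stated fallback if the model does not converge. Report the Week 48 contrast, and enter early-termination values at their actual visit time.

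Keep ANCOVA for histology, which has one post-baseline biopsy. Keep it also for MRI-HFF, because Section 7.2.2.2 limits the Week 24 scan to the interim subjects. HOMA is calculated at only two treatment visits up to Week 48 (Section 7.2.3.6), so the text should say which model applies to it.

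The cost is a few sentences, slightly more modelling work and possible convergence problems. No new data are needed, the software already named in Section 9.4 suffices, and the primary endpoint is unaffected. Because the protocol text names ANCOVA, change it there before unblinding so that the SAP does not have to depart from it.

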9.8.3 Exploratory Efficacy Endpoints

Descriptive statistics will be presented for each time point at which the variable is measured (see **Table 1**) for the exploratory efficacy endpoints. Binary exploratory efficacy endpoints will be analyzed with the same method (stratified Cochran-Mantel-Haenzel test) as the primary efficacy endpoint. Continuous exploratory efficacy endpoints will be analyzed with an ANCOVA model with change from baseline as the outcome variable; treatment group, presence or absence of T2DM at baseline, and baseline NAS separated into 2 groups (NAS={4,5} or NAS={6,7,8}) as factors and baseline values as a covariate. Endpoints include:

- Change from baseline to Week 48 on liver histology as measured by the SAF scoring components: Steatosis (S), Activity (A), and Fibrosis (F)
- Change from baseline to Week 48 on anthropomorphic measures:
 - body weight
 - BMI
 - waist circumference
 - waist-hip ratio
- Change from baseline to Week 48 in subjects with T2DM on homeostasis measured by:
 - Homeostasis model assessment -IR (HOMA-IR)
 - HOMA-beta cell function (HOMA-%B)

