9.8 Efficacy Analyses

All efficacy analyses will be based on the FAS and all statistical tests will be 2-sided hypothesis tests performed at the 10% level of significance. Also, all confidence intervals will be 2-sided confidence intervals, unless otherwise stated.

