9. Current use of any medication (including over-the-counter, herbal, or homeopathic preparations) that could affect the action, absorption, or disposition of the IP, or clinical or laboratory assessment. (Current use is defined as use within 14 days of Screening). Patients currently taking insulin will not be excluded; however, they must be on a stable dose for at least 30 days prior to Screening. Also refer to Section [5.2.2](#), Prohibited Treatment.
10. Use of drugs, herbs or supplements historically associated with causing or worsening NAFLD/NASH for less than 6 months prior to liver biopsy, or initiated any time after liver biopsy performed, including the use of total parenteral nutrition (TPN). Also refer to Section [5.2.2](#), Prohibited Treatment.
11. Serum AST > 5 times upper limit of normal (ULN) at Screening.
12. Serum ALT > 5 times ULN at Screening.
13. Elevated serum creatinine ≥ 2.0 mg/dL.
14. International normalized ratio (INR) > 1.3
15. TB $\geq 2.0 \times$ ULN at Screening (Except for documented Gilbert's syndrome with bilirubin levels 20 μ mol/L to 90 μ mol/L (1.2 to 5.3 mg/dL) and with a ratio of unconjugated/conjugated bilirubin that is commensurately higher).
16. Platelet count $< 130 \times 10^9/L$
17. Medical history of impaired hemostasis or use of anticoagulant medication (low-dose, ie 81 mg, aspirin (ASA) will be allowed).
18. Uncontrolled thyroid disease.
19. Type 1 diabetes mellitus.

20. Known or suspected intolerance or hypersensitivity to the IP, closely-related compounds, or any of the stated ingredients.
21. Known history of alcohol or other substance abuse within the last year or at any time during the study based on investigator's discretion. Refer to Section [7.2.3.8](#), Drug and Alcohol Screening. Weekly alcohol intake greater than 21 grams/day for males and 14 grams/day for females on average or inability to reliably quantify alcohol consumption based on investigator's judgment.
22. Within 6 months of MRI and liver biopsy:
 - Have used any IP
 - Have been enrolled in a clinical study (including vaccine studies) that, in the investigator's opinion, may impact this Shire-sponsored study
23. Inability to safely obtain a liver biopsy.
24. The anticipated need for a surgical procedure during the study that could interfere with the treatment.
25. Known positivity for human immunodeficiency virus (HIV) infection.

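### The HOMA and fasting insulin analyses make no provision for insulin users, in whom these measures do not cleanly reflect the subject's own insulin resistance or secretion

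*Protocol*

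**What the plan says.** - **HOMA population and model.** Section 9.8.3 gives the endpoint as "Change from baseline to Week 48 in subjects with T2DM on homeostasis measured by" HOMA-IR and HOMA-%B. The model is an ANCOVA on change from baseline with treatment, T2DM status, NAS group and the baseline value. Insulin use is not a term.
- **Fasting insulin.** Section 9.8.2 lists "insulin levels" among the metabolic secondary endpoints, with the same form of ANCOVA.
- **Analysis set.** Section 9.8 states: "All efficacy analyses will be based on the FAS". Section 9.7 builds the FAS from the Safety Analysis Set plus at least one post-baseline efficacy assessment, without regard to insulin use.
- **Measurement.** Section 7.2.3.6: "Insulin will be tested at screening, baseline, at Visit 4 and Visits 6 through 10". The same section adds: "HOMA-IR and HOMA-%B: will be calculated programmatically from serum glucose tested at screening, baseline, Visits 7, 9, and 10". No exception is made for insulin users, and C-peptide is in neither laboratory list (Sections 7.2.3.5 and 7.2.3.6).
- **Eligibility.** Section 4.2 in the Amendment 1 text: "Patients currently taking insulin will not be excluded; however, they must be on a stable dose for at least 30 days prior to Screening". Section 4.2 of the initial protocol carries the same permission. "Type 1 diabetes mellitus" is an exclusion criterion. Section 4 of Amendment 2 is not in the part of the document shown.
- **Randomization.** Section 6.2.2 stratifies by T2DM and NAS group, not by insulin use.

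**The concern.** HOMA combines fasting glucose and fasting insulin and reads the insulin value as the subject's own output. In someone who injects insulin, the assay may also pick up the injected product, and the glucose value has been lowered by it. The two indices then no longer describe that person's insulin resistance or beta-cell function cleanly, and the fasting insulin endpoint has the same weakness.

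With type 1 diabetes excluded, insulin users would be expected to have T2DM. Restricting HOMA to T2DM therefore concentrates them in that analysis. Nothing collected allows the subject's own secretion to be separated out afterwards. At stake is how well the trial can read an effect on insulin resistance, which the background section (1.2 in the Amendment 1 text) names as a potential action of volixibat.

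**Working it through.** The protocol gives no sample size, power or expected effect for HOMA or fasting insulin, so there is no figure of its own to reproduce. The check is a reading of the text followed by a conditional calculation.

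**1. Who enters each analysis, as written**

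| Step | HOMA-IR, HOMA-%B | Fasting insulin |
|---|---|---|
| Analysis set (9.7, 9.8) | FAS | FAS |
| Further restriction (9.8.3, 9.8.2) | T2DM only | none |
| Insulin users removed? | no | no |
| Insulin use in the model? | no | no |
| Insulin use as a stratum (6.2.2)? | no | no |

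If insulin users remain eligible, they enter both analyses.

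**2. How many, under assumptions**

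From Section 9.6: 67 completers per group. Assumed, because the documents give neither: 40-60% of subjects have T2DM, and a fraction f = 10-30% of those use insulin.

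- T2DM subjects per arm: 67 × 0.40 = 26.8 to 67 × 0.60 = 40.2, about 27 to 40.
- Insulin users per arm: 67 × 0.40 × 0.10 = 2.7 to 67 × 0.60 × 0.30 = 12.1, about 3 to 12.

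**3. Information lost for HOMA, worst case**

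Suppose insulin users show no treatment signal at all and the variance is unchanged. Keeping them multiplies the mean difference by (1 − f), so the effective sample is multiplied by (1 − f)². Setting them aside keeps the full difference in a sample multiplied by (1 − f).

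| f | Kept: (1 − f)² | Set aside: 1 − f |
|---|---|---|
| 0.10 | 0.81 | 0.90 |
| 0.30 | 0.49 | 0.70 |

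For fasting insulin, analysed in the whole FAS, the same assumptions give f = 0.40 × 0.10 = 4% to 0.60 × 0.30 = 18%. Then (1 − f)² runs from 0.96² = 0.92 to 0.82² = 0.67, against 0.96 to 0.82 if set aside.

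**4. What injected insulin can do to one subject's HOMA (illustration)**

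The protocol gives no HOMA formula. Assume the closed forms HOMA-IR = G × I / 22.5 and HOMA-%B = 20 × I / (G − 3.5), with fasting glucose G = 8 mmol/L and the subject's own insulin 15 µU/mL.

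- No injected contribution: HOMA-IR = 8 × 15 / 22.5 = 5.3; HOMA-%B = 20 × 15 / 4.5 = 67.
- Assay reads 5 µU/mL more (I = 20): 7.1 and 89. The injected share of measured insulin is 5/20 = 25%.
- Assay reads 40 µU/mL more (I = 55): 19.6 and 244. The share is 40/55 = 73%.

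The 5-40 µU/mL range is assumed. Whether the assay detects the injected product is not stated.

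**The case against.** The strongest reply is that this belongs in the SAP. Section 9.4 leaves analysis definitions, and the handling of missing, unused and spurious data, to that document, and a rule on which HOMA values are evaluable could sit there without contradicting the protocol. This stands in part: the SAP could supply the restriction. But the protocol does more than stay silent. It names the HOMA population, the analysis set and the model terms, and the population it names is less suitable than one defined by baseline insulin use.

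Second, the permission for insulin users comes from earlier protocol text, because Section 4 of Amendment 2 is not shown. That stands, and it makes the point conditional. Both versions of Section 4.2 that can be seen carry the permission.

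Third, a constant injected contribution is partly removed by analysing change from baseline with the baseline value as covariate. That also stands, and it is why the no-signal calculation is only a worst case.

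A reader might infer that the comparison between arms is biased, or that a drug effect would be confused with insulin titration. The documents do not establish this. Randomization balances baseline insulin use in expectation, so bias needs dose changes that differ by arm, and nothing shown says they would. The Amendment 1 text also asks subjects to stay within the eligibility criteria during the study (Section 4.3) and has investigators discuss relevant changes in concomitant medication with the medical monitor and then the sponsor (Section 5.2.1). Neither is an explicit on-study rule for insulin, but they make free titration less likely.

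A reader might also infer that every value after a start of insulin should be dropped. That would condition on an event after randomization; if starts differed by arm, dropping the values could itself introduce bias.

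**Conclusion.** The point holds as a minor one, provided insulin users remain eligible under Amendment 2. As written, Sections 9.8.2 and 9.8.3 take their fasting insulin and HOMA values into the efficacy analyses with no restriction or adjustment, and those values do not cleanly measure what the endpoints are meant to measure.

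The main consequence is noise and dilution. Its size is unknown, since neither the share of insulin users nor the assay's response to injected insulin is given. The worst-case HOMA figures, 81-49% of the effective sample if insulin users are kept against 90-70% if set aside, rest on an assumed 10-30% share and on no treatment signal in any of them. HOMA is exploratory and fasting insulin secondary. The primary histology analysis and the stated sample size are unaffected.

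**What to change.** - Confirm whether Amendment 2 still admits insulin users.
- In Section 9.8.3, state that HOMA-IR and HOMA-%B are analysed in subjects with T2DM who are not receiving insulin at baseline.
- In Section 9.8.2, restrict the fasting insulin endpoint to subjects not receiving insulin at baseline.
- Present the insulin users' values descriptively, by arm.
- For insulin started on study, keep the values in the main result and prespecify a sensitivity analysis that sets them aside, reported beside it.

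Baseline insulin use is fixed before randomization, so the restriction does not disturb the comparison between arms. Concomitant medication is already collected at every visit (Section 7.1.3), so no new data are needed. This is a change to the analysis text only. The cost is about a sentence in each section and somewhat fewer subjects in these analyses: under the assumptions above, about 3 to 12 of 27 to 40 T2DM subjects per arm for HOMA.
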